15.0 STATISTICAL SOFTWARE

Statistical analyses will be performed using version [REDACTED]
[REDACTED]

16.0

DATA HANDLING CONVENTIONS

16.1

SUMMARY STATISTICS

The following statistical summaries will be presented for each type of data. Further details are specified in the tables, figures, and listings shells.

- Continuous variables will be summarized by descriptive statistics (number of patients, mean, standard deviation (SD), median, Q1 and Q3, minimum, and maximum values).
- Categorical variables will be summarized by frequency distributions (counts and percentages).
- Time-to-event data will be summarized by showing the number of patients, number of patients experiencing the event of interest, estimates of the median, 1st quartile and 3rd quartile using the Kaplan Meier estimate as well as a 95% CI for the median

16.2

VISIT TIME WINDOWS

Table 16.2-1 presents the visits assigned for efficacy and safety analyses and the corresponding range of treatment days (window) during which an actual visit may occur.

Table 16.2-1. Visit Time Windows

Derived Visit	Target Day	Analysis Visit Window
Baseline		<= Day 0 ^a and before the first study IP
Double Blind Treatment Period (DBTP)		
Post First Study IP ^c	Day 0	Post the first study IP on Day 0
Day 1	Day 1	Day 1
Day 7	Day 7	Start: Day 2
		End: the Day 7 dosing (Visit 4) date or Day 10 (if no Day 7 dosing) ^b
Week 2	Day 14	Start: 1 day after the Day 7 window ends
		End: the Week 2 (Visit 5) dosing date or Day 17 (if no Week 2 dosing) ^b
Week 3	Day 21	Start: 1 day after the Week 2 window ends
		End: the Week 3 (Visit 6) dosing date or Day 24 (if no Week 3 dosing) ^b
Week 4	Day 28	Start: 1 day after the Week 3 window ends
		End: the Week 4 (Visit 7) dosing date or Day 31 (if no Week 4 dosing) ^b

Table 16.2–1. Visit Time Windows

Week 5	Day 35	Start: 1 day after the Week 4 window ends
		End: the Week 5 (Visit 8) dosing date or Day 38 (if no Week 5 dosing) ^b
Week 6	Day 42	Start: 1 day after the Week 5 window ends
		End: End of DBTP (the study exit date of DBTP)
Safety Follow-up Period (SFP)		
Week 8	Day 56	Within the safety follow-up phase
End of SFP: Final or termination visit during SFP		

^a Day 0 is the date of the first dose of study treatment; baseline is defined as the last non-missing observations prior to first dose of study treatment.

^b Dosing visit is the nominal visit reported in CRF. A patient is scheduled to receive the 1st dose on day 0, the 2nd dose at week 1, and will be weekly administered until week 5. If a patient skipped a scheduled re-treatment dosing at a week, the dosing date will be treated as missing for that week.

If a patient has 2 or more non-missing assessment within the same window, the assessment closest to the target day will be used for analysis; if the 2 closest assessments are equidistant to the target day, the later one will be used for analysis.

16.3 REPEATED OR UNSCHEDULED ASSESSMENTS OF SAFETY PARAMETERS

If a patient has repeated assessments before the start of the first treatment, the results from the final non-missing assessment made prior to the start of the study treatment will be used as baseline. If end-of-study assessments are repeated or if unscheduled visits occur, the last non-missing postbaseline assessment will be used as the end-of-study assessment for generating summary statistics. However, all postbaseline assessments will be used for PCS value determinations, and all assessments will be presented in the data listings.

16.4 MISSING SEVERITY ASSESSMENT FOR ADVERSE EVENTS

If severity is missing for an AE that started before the date of the first dose of study treatment, an intensity of mild will be assigned. If severity is missing for an AE that started on or after the date of the first dose of study treatment, an intensity of severe will be assigned. The imputed values for severity assessment will be used for the incidence summary; the values will be shown as missing in the data listings.

16.5 MISSING CAUSAL RELATIONSHIP TO STUDY DRUG FOR ADVERSE EVENTS

If the causal relationship to the study treatment is missing for an AE that started on or after the date of the first dose of study treatment, a causality of yes will be assigned. The imputed values for causal relationship to study treatment will be used for the incidence summary; the values will be shown as missing in the data listings.

16.6 MISSING DATE INFORMATION FOR ADVERSE EVENTS

The following imputation rules only apply to cases in which the start date for AEs is incomplete (i.e., partly missing).

Missing month and day

- If the year of the incomplete start date is the same as the year of the first dose of study treatment, the month and day of the first dose of study treatment will be assigned to the missing fields
- If the year of the incomplete start date is before the year of the first dose of study treatment, *December 31* will be assigned to the missing fields
- If the year of the incomplete start date is after the year of the first dose of study treatment, *January 1* will be assigned to the missing fields

Missing month only

- If only the month is missing, the day will be treated as missing and both the month and the day will be replaced according to the above procedure

Missing day only

- If the month and year of the incomplete start date are the same as the month and year of the first dose of study treatment, the day of the first dose of study treatment will be assigned to the missing day
- If either the year of the incomplete start date is before the year of the date of the first dose of study treatment or if both years are the same but the month of the incomplete start date is before the month of the date of the first dose of study treatment, the last day of the month will be assigned to the missing day
- If either the year of the incomplete start date is after the year of the date of the first dose of study treatment or if both years are the same but the month of the incomplete start date is after the month of the date of the first dose of study treatment, the first day of the month will be assigned to the missing day

If the stop date is complete and the imputed start date as above is after the stop date, the start date will be imputed by the stop date.

If the start date is completely missing and the stop date is complete, the following algorithm will be used to impute the start date:

- If the stop date is after the date of the first dose of study treatment, the date of the first dose of study treatment will be assigned to the missing start date
- If the stop date is before the date of the first dose of study treatment, the stop date will be assigned to the missing start date

16.7 MISSING DATE INFORMATION FOR PRIOR OR CONCOMITANT MEDICATIONS

For prior or concomitant medications, incomplete (ie, partly missing) start dates and/or stop dates will be imputed. When the start date and the stop date are both incomplete for a patient, the start date will be imputed first.

16.7.1 Incomplete Start Date

The following rules will be applied to impute the missing numeric fields for an incomplete prior or concomitant medication start date. If the stop date is complete (or imputed) and the imputed start date is after the stop date, the start date will be imputed using the stop date.

Missing month and day

- If the year of the incomplete start date is the same as the year of the first dose of study treatment, the month and day of the first dose of study treatment will be assigned to the missing fields
- If the year of the incomplete start date is before the year of the first dose of study treatment, *December 31* will be assigned to the missing fields
- If the year of the incomplete start date is after the year of the first dose of study treatment, *January 1* will be assigned to the missing fields

Missing month only

- If only the month is missing, the day will be treated as missing and both the month and the day will be replaced according to the above procedure

Missing day only

- If the month and year of the incomplete start date are the same as the month and year of the first dose of study treatment, the day of the first dose of study treatment will be assigned to the missing day
- If either the year of the incomplete start date is before the year of the date of the first dose of study treatment or if both years are the same but the month of the incomplete start date is before the month of the date of the first dose of study treatment, the last day of the month will be assigned to the missing day.
- If either the year of the incomplete start date is after the year of the date of the first dose of study treatment or if both years are the same but the month of the incomplete start date is after the month of the date of the first dose of study treatment, the first day of the month will be assigned to the missing day

16.7.2 Incomplete Stop Date

The following rules will be applied to impute the missing numeric fields for an incomplete prior or concomitant medication stop date. If the date of the last dose of study treatment is missing, impute it as described in Section 16.4. If the imputed stop date is before the start date (imputed or nonimputed start date), the imputed stop date will be equal to the start date.

Missing month and day

[figure not shown]
- If the year of the incomplete stop date is the same as the year of the last dose of study treatment, the month and day of the last dose of study treatment will be assigned to the missing fields
- If the year of the incomplete stop date is before the year of the last dose of study treatment, *December 31* will be assigned to the missing fields
- If the year of the incomplete stop date is after the year of the last dose of study treatment, *January 1* will be assigned to the missing fields

Missing month only

- If only the month is missing, the day will be treated as missing and both the month and the day will be replaced according to the above procedure

Missing day only

- If the month and year of the incomplete stop date are the same as the month and year of the last dose of study treatment, the day of the last dose of study treatment will be assigned to the missing day
- If either the year of the incomplete stop date is before the year of the date of the last dose of study treatment or if both years are the same but the month of the incomplete stop date is before the month of the date of the last dose of study treatment, the last day of the month will be assigned to the missing day
- If either the year of the incomplete stop date is after the year of the date of the last dose of study treatment or if both years are the same but the month of the incomplete stop date is after the month of the date of the last dose of study treatment, the first day of the month will be assigned to the missing day

[REDACTED]

[REDACTED]

17.0 **REFERENCES**

Kenward MG and Roger JH. Small sample inference for fixed effects from restricted maximum likelihood. *Biometrics* 1997; 53: 983-997.

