Signed informed consent from the patient or the patient's legally authorized representative will be obtained before any study-related procedures are begun. Patients will wash out any previous ADT and/or prohibited medications during the screening period. Patients meeting the eligibility criteria at the end of Visit 2 will be randomized in a ratio of 1:1:1 to one of the three treatment arms: rapastinel 900 mg IV weekly, rapastinel 450 mg IV weekly, or placebo IV weekly. The double-blind treatment period (DBTP) starts with the first dose of study treatment. Upon completion of the DBTP, patients may be eligible to enter the extension study. Patients who do not enter the extension study will enter a 2-week safety follow-up period. Efficacy and safety assessments will be conducted at the clinic 1 day following the treatment day in the 1st week and at the ends of weeks 1, 2, 3, 4, 5 and 6 of the DBTP. Patients prematurely discontinuing from the study, regardless of cause, will be seen for a final evaluation. The schedule of evaluations for Study RAP-MD-32 is presented in [Table 4-1](#).

[figure not shown]

[figure not shown]

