7.1 PROTOCOL DEVIATIONS

Protocol deviations will be defined in Protocol Deviation Requirement Specification, including the classification of significance vs. non-significance. The number and percentage of patients with significant protocol deviations will be summarized by treatment group for all randomized patients. A listing for all significant protocol deviations will be provided.

8.0

DEMOGRAPHICS AND OTHER BASELINE CHARACTERISTICS

Demographic parameters (age; race; ethnicity; sex), baseline characteristics (weight; height; and body mass index, calculated as weight [kg]/(height [m])²) will be summarized descriptively by treatment group for the mITT population.

Medical and surgical histories, and psychiatric history will be coded using the Medical Dictionary for Regulatory Activities (MedDRA) dictionary and summarized by treatment group for the Safety Population.

Prior medication is defined as any medication taken before the date of the first dose of randomized IP. *Concomitant medication* is defined as any medication taken on or after the date of the first dose of randomized IP. Concomitant medications started after the last visit of the DBTP will not be included in the summaries. If any medication is taken before the date of the first dose of randomized IP and continues after initiation of randomized IP, it will be considered as both a prior and concomitant medication. The *World Health Organization (WHO) Drug Dictionary Enhanced* will be used to code medications.

Both prior and concomitant medication use, and previous treatment with psychotropic medication will be summarized by treatment group and Anatomical Therapeutic Chemical (ATC) code for the Safety Population.

Nondrug psychiatric treatment will be summarized by treatment group for the Safety Population.

9.0

EXTENT OF EXPOSURE AND TREATMENT COMPLIANCE

9.1

EXTENT OF EXPOSURE

The total number of IV doses actually received by a patient during the double-blind treatment period will be summarized by treatment group for the safety population.

IV administration notes including site reaction at placement of IV, reaction to adhesive, infusion interruption, failure of administration device, perceptual disturbances or other conditions based on mental status assessment are collected. For each item, the number and percentage of patients who had a 'yes' response will be summarized by treatment group and visit for the Safety Population.

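### Sections 16.7.1 and 16.7.2 correct the same pair of partial medication dates in opposite directions; for one date pattern, a drug stopped before the first dose is tabulated as concomitant only

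*SAP*

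**What the plan says.** Section 16.7 of the SAP sets the order for medication dates: "When the start date and the stop date are both incomplete for a patient, the start date will be imputed first".

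Each subsection then has its own rule for a start that ends up after the stop.

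- Section 16.7.1 (start dates) sets this condition on the stop date, with its consequence: "complete (or imputed) and the imputed start date is after the stop date, the start date will be imputed using the stop date".
- Section 16.7.2 (stop dates) sets the reverse: "imputed stop date is before the start date (imputed or nonimputed start date), the imputed stop date will be equal to the start date".

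For a start with month and day missing, in the same year as the first dose, 16.7.1 says "the month and day of the first dose of study treatment will be assigned to the missing fields". For a stop with only the day missing, in a month before the month of the last dose, 16.7.2 assigns the last day of the recorded month.

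Section 8.0 turns the dates into table entries. A medication is prior if taken before the first-dose date. A concomitant medication "is defined as any medication taken on or after the date of the first dose of randomized IP". Both kinds are summarized by treatment group and ATC code for the Safety Population.

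**The concern.** Each conflict rule expressly covers the case where the other date is imputed, so by wording alone neither gives way. For the same pair of dates, one moves the start and the other moves the stop. A programmer who follows the order in 16.7 lets 16.7.2 decide. One who honours the words on an imputed stop date in 16.7.1 gets the opposite result.

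Following the stated order can also let an imputed start overwrite a stop month that the site recorded. If that moves the stop from before the first dose to the first-dose date, the drug enters the concomitant table and leaves the prior table. Both entries are then wrong. In a monotherapy trial, readers will look at these tables when they ask what else patients were taking in each arm.

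**Working it through.** The SAP gives no figure to reproduce, so the check applies its rules to concrete records.

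**Inputs.** The rules are those of 16.7, 16.7.1, 16.7.2 and 8.0 as set out above. For illustration I assume a first dose on 10 Jul 2019 and a last dose 35 days later, on 14 Aug 2019 (weekly dosing from Day 0 to Week 5, per the notes to Table 16.2-1).

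**Record: start 2019 (month and day missing), stop Mar 2019 (day missing).**

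1. The start is imputed first. Its year equals the first-dose year, so start = 10 Jul 2019. No imputed stop exists yet, so the 16.7.1 conflict rule has nothing to act on.
2. The stop is imputed next. March precedes the last-dose month, so stop = 31 Mar 2019.
3. The stop is before the start, so 16.7.2 sets stop = 10 Jul 2019. The recorded month is overridden by 30 + 31 + 30 + 10 = 101 days.
4. Section 8.0: the start is not before 10 Jul, so the drug is not prior. The stop is on 10 Jul, so it is concomitant.

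If the 16.7.1 rule is applied instead, start = stop = 31 Mar 2019, and the drug is prior only. That agrees with everything recorded.

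**How far it reaches (same dosing dates).**

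| Start recorded | Stop recorded | Imputed dates before any correction | Class under 16.7.2 rule | Class under 16.7.1 rule |
|---|---|---|---|---|
| 2019 | Mar 2019 | 10 Jul 2019 / 31 Mar 2019 | concomitant | prior |
| 2018 | Mar 2018 | 31 Dec 2018 / 31 Mar 2018 | prior | prior |
| 2018 | Mar 2019 | 31 Dec 2018 / 31 Mar 2019 | prior (no conflict) | prior |
| Jan 2019 | Mar 2019 | 31 Jan 2019 / 31 Mar 2019 | prior (no conflict) | prior |
| 2019 | 2019 | 10 Jul 2019 / 14 Aug 2019 | concomitant (no conflict) | concomitant |

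If the stop is complete, say 15 Mar 2019, only 16.7.1 applies. The start moves to 15 Mar and the drug stays prior.

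**Enumeration.** I took all logically possible pairs of partial dates with years 2017 to 2019, starts no later than the first-dose month, first dose on the 16th of each month from January to November 2019, and last dose 35 days later. This gives 8,624 patterns.

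- The two rules conflict in 297.
- Of these, 11 stop months x 2 earlier years x 11 first-dose months = 242 have a start known only to an earlier year and a stop in January to November of that year. The dates differ but the drug is prior either way.
- The other 0 + 1 + ... + 10 = 55 have a start known only to the first-dose year and a stop in an earlier month of that year. All 55 change from prior to concomitant.
- 242 + 55 = 297.

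The share 55/8,624 = 0.6% counts date patterns, not patients or records.

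**The case against.** The strongest reply has three parts. First, Section 16.7 fixes an order, so a careful programmer gets one answer. Second, placing an uncertain stop late is cautious, because it avoids hiding on-treatment use. Third, the pattern is narrow and the tables are descriptive. Section 8.0 also summarizes previous psychotropic treatment separately, and Section 7.1 covers significant protocol deviations.

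The third part stands and limits the weight of the point. The first stands only in part: the order does select a rule, but when both dates are partial it leaves the reference to an imputed stop in 16.7.1 with nothing to do, and the rule it selects gives the wrong entry. The second does not answer the point. Caution can justify a late date where the date is unknown. It does not justify replacing a recorded month with an imputed date, or removing from the prior table a drug that was taken only before the first dose. Where the stop date is complete, 16.7.1 already lets the recorded date prevail, and so does the adverse-event rule in 16.6.

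A reader might infer more, in two ways that the document does not support.

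- *That washed-out antidepressants in general will appear as on-treatment drugs and vanish from the prior table.* The Introduction does say "Patients will wash out any previous ADT and/or prohibited medications during the screening period", but the misclassification depends on the date pattern above. With an earlier start year, a start month recorded before the first-dose month, or a complete stop date, the drug keeps its prior status.
- *That tying partial stop dates to the last dose is itself an error.* It is a cautious convention, contradicts nothing in the SAP, and does not remove prior status when the start is earlier.

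**Conclusion.** The contradiction is real, and in the stated order it gives a wrong table entry for one date pattern: start known only to the first-dose year, stop known to an earlier month of that year. Every such record is shown as concomitant only instead of prior only. Other conflicting records with a start in an earlier year get different dates but the same class.

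The effect is confined to the prior and concomitant medication summaries. A reader might infer a threat to the efficacy result, but neither the mITT definition (6.2) nor the MMRM (10.1) uses these flags in the visible text. How many records have this pattern is not in the document, so no size in patients can be given. Redacted lines follow 16.7.2; the conclusion rests on the visible text, where nothing resolves the conflict. The point is worth correcting because the repair is small, but it is a minor one.

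**What to change.** Delete the conflict sentences in 16.7.1 and 16.7.2 and put one check in 16.7, run after both dates have been imputed:

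> If the imputed start is after the stop, move only the date whose new value still agrees with its own recorded month and year. Never change a complete date or override a recorded month or year. If both moves agree with the recorded parts, apply [one named default].

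Letting 16.7.1 always prevail would not do, because it fails on the mirror case. Take start Sep 2019 and stop 2019, with the dosing dates above. The start is imputed as 1 Sep and the stop as 14 Aug. Moving the start to 14 Aug overwrites the recorded September. It would also put the drug in the concomitant table when it started after the Week 6 target day (10 Jul + 42 days = 21 Aug). If the last visit was near that day, Section 8.0 excludes the drug.

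Under the proposed check the two records resolve as follows.

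| Start recorded | Stop recorded | Correction |
|---|---|---|
| 2019 | Mar 2019 | start = 31 Mar 2019 |
| Sep 2019 | 2019 | stop = 1 Sep 2019 |

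Both make good test records for the program. If neither move fits, the recorded parts contradict each other and the record should go to query. The order of imputation in 16.7 can stay. The cost is a short SAP edit and a few lines of derivation code, with no new data.
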